6.1.1.2. Sasanlimab (PF-06801591)

For participants in Part 1B and Part 2, qualified and trained investigator site personnel will administer sasanlimab at a fixed dose. See [Section 8.2.7](#) for local site injection tolerability assessment. In the investigational combination therapy with PF-07265028, sasanlimab 300 mg (50 mg/mL), will be administered SC Q4W to the abdomen. Sasanlimab should be administered to 2 or more different quadrants of the abdomen (with preference given to the lower quadrants when possible); 1 or 2 injections per quadrant. If SC injections in the abdominal location are not possible, SC injections can be administered in a distributed manner in the thighs. SC injections in the upper extremities (eg, deltoid, upper and lower arm) are not permitted. Sasanlimab SC injection will be administered at least 30 minutes after administration of PF-07265028. Additional guidance on SC injection site locations is provided in [Appendix 16 Section 10.16](#). For specific instructions on the handling and preparation instructions of study intervention, refer to the Product Specific IP manual. See [Section 8.2.7](#) for local site injection tolerability assessment.

Study staff should refer to the IP manual for specific instructions on the preparation and handling of the study intervention.

A cycle is defined as the time from Day 1 dose to the next Day 1 dose. Participants will receive a single dose of sasanlimab on Day 1 of each cycle.

6.2. Preparation, Handling, Storage and Accountability

1. The investigator or designee must confirm appropriate temperature conditions have been maintained during transit for all study interventions received and any discrepancies are reported and resolved before use of the study intervention.
2. Only participants enrolled in the study may receive study intervention and only authorized site staff may supply or administer study intervention. All study interventions must be stored in a secure, environmentally controlled, and monitored (manual or automated recording) area in accordance with the labeled storage conditions with access limited to the investigator and authorized site staff. At a minimum, daily minimum and maximum temperatures for all site storage locations must be documented and available upon request. Data for nonworking days must indicate the minimum and maximum temperatures since previously documented for all site storage locations upon return to business.
3. Any excursions from the study intervention label storage conditions should be reported to Pfizer upon discovery along with any actions taken. The site should actively pursue options for returning the study intervention to the storage conditions described in the labeling, as soon as possible. Once an excursion is identified, the study intervention must be quarantined and not used until Pfizer provides permission to use the study intervention. Specific details regarding the definition of an excursion and information the site should report for each excursion will be provided to the site in the IP manual.

4. Any storage conditions stated in the SRSD will be superseded by the storage conditions stated on the label.
5. Study interventions should be stored in their original containers.
6. Site staff will instruct participants on the proper storage requirements for take-home study intervention.
7. See the IP manual for storage conditions of the study intervention.
8. The investigator, institution, or the head of the medical institution (where applicable) is responsible for study intervention accountability, reconciliation, and record maintenance (ie, receipt, reconciliation, and final disposition records), such as the IPAL or sponsor-approved equivalent. All study interventions will be accounted for using a study intervention accountability form/record.
9. All PF-07265028 that is taken home by the participant, both used and unused bottles, must be returned to the investigator by the participant. Returned study intervention must not be re-dispensed to the participants.
10. Further guidance and information for the final disposition of unused study interventions are provided in the IP manual. All destruction must be adequately documented. If destruction is authorized to take place at the investigator site, the investigator must ensure that the materials are destroyed in compliance with applicable environmental regulations, institutional policy, and any special instructions provided by Pfizer.

Upon identification of a product complaint, notify the sponsor within 1 business day of discovery as described in the IP manual.

6.2.1. Preparation and Dispensing

Bottles and Vials:

A qualified staff member will dispense the study intervention using the IRT system via unique container numbers in the bottles and vials provided, in quantities appropriate according to the [SoA](#). A second staff member will verify the dispensing. The participant should be instructed to maintain the product in the bottle or vial provided throughout the course of dosing and return the [bottle, vials, or blister cards, as appropriate] to the site at the next study visit.

See the IP manual for instructions on how to prepare the study intervention for administration. Study intervention should be prepared and dispensed by an appropriately qualified and experienced member of the study staff (eg, physician, nurse, physician's assistant, nurse practitioner, pharmacy assistant/technician, or pharmacist) as allowed by local, state, and institutional guidance. A second staff member will verify the dispensing.

Only qualified personnel who are familiar with procedures that minimize undue exposure to themselves and to the environment should undertake the preparation, handling, and safe disposal of biologic agents.

6.3. Measures to Minimize Bias: Randomization and Blinding

6.3.1. Allocation to Study Intervention

This is an open-label Phase 1 study that will not be randomized. The investigator's knowledge of the treatment should not influence the decision to enroll a particular participant or affect the order in which participants are enrolled.

No participant will receive study intervention until the investigator or designee has received the following information in writing from the sponsor:

- Confirmation of the participant's enrollment;
- Specification of the dose level for that participant and;
- Permission to proceed with dosing the participant.

Study intervention will be dispensed at the study visits summarized in the [SoA Table 1](#).

Returned study intervention must not be redispensed to the participant.

Allocation of participants to treatment groups will proceed through sponsor or designee and will include the participant number and randomization number. The site staff will e-mail a complete Registration Form to the designated sponsor study team member or designee. The sponsor will assign a participant identification number and supply this number to the site. The form must be stored in the site's files. The participant identification number will be used on all study-related documentation at the site.

Returned study intervention must not be re-dispensed to the participants.

This is an open-label study; the study intervention dose will be determined by the sponsor and dispensed to the participant using an IRT. The IRT will assign a kit number for study intervention administration for each participant.

The study-specific IRT reference manual and IP manual will provide the contact information and further details on the use of the IRT system.

6.4. Study Intervention Compliance

When the individual dose for a participant is prepared from a bulk supply, the preparation of the dose will be confirmed by a second qualified member of the study site staff. When participants are dosed at the site, they will receive study intervention directly from the investigator or designee, under medical supervision. The date and time of each dose administered in the clinic will be recorded in the source documents and recorded in the CRF.

The dose of study intervention and study participant identification will be confirmed at the time of dosing by a member of the study site staff other than the person administering the study intervention.

The site will complete the required dosage Preparation Record located in the IP manual. The use of the Preparation Record is preferred, but it does not preclude the use of an existing appropriate clinical site documentation system. The existing clinical site's documentation system should capture all pertinent/required information on the preparation and administration of the dose. This may be used in place of the Preparation Record after approval from the sponsor and/or designee.

When participants self-administer study intervention(s) at home, compliance with study intervention will be assessed at each visit. Compliance will be assessed counting returned tablets/capsules during the site visits and documented in the source documents and CRF. Deviation(s) from the prescribed dosage regimen should be recorded in the CRF.

A record of the number of tablets/capsules/ dispensed to and taken by each participant must be maintained and reconciled with study intervention and compliance records. Intervention start and stop dates, including dates for intervention delays and/or dose reductions, will also be recorded in the CRF.

6.5. Dose Modification

Dose modifications may occur in 1 of 3 ways:

- Within a cycle: dosing interruption until adequate recovery and dose reduction, if required, during a given treatment cycle;
- Between cycles: next cycle administration may be delayed due to persisting toxicity when a new cycle is due to start;
- In the next cycle: dose reduction may be required in a subsequent cycle based on toxicity experienced in the previous cycle.

The decision to proceed to the next dose level of PF-07265028 (either an increase or a decrease) will be made by the study team and the investigators based on safety, tolerability, and preliminary PK and/or pharmacodynamics data obtained in all participants at the prior dose level.

The dosing schedule may also be adjusted to expand a dosing cohort to further evaluate safety, PK, and/or pharmacodynamics findings at a given dose level or to add cohorts to evaluate additional dose levels. The study procedures for these additional participant(s)/cohort(s) will be the same as that described for other study participants/cohorts.

Every effort should be made to administer study intervention on the planned dose and schedule. In the event of significant toxicity, dosing of PF-07265028 may be delayed and/or reduced as described below. In the event of multiple toxicities, dose modification should be based on the worst toxicity observed and attribution for the combination treatment (for combination therapy). Participants are to be instructed to notify investigators at the first occurrence of any adverse symptom. In addition to dose modifications, investigators are encouraged to employ best supportive care according to local institutional clinical practices.

Toxicities potentially related to PF-07265028 should be managed according to the dose modifications described in Table 8.

Table 8. Dose Modifications for PF-07265028-Related Toxicity

Toxicity	Grade 1	Grade 2	Grade 3	Grade 4
Nonhematologic	Continue at the same dose level.	Continue at the same dose level.	Withhold dose until toxicity is Grade ≤ 1 , or has returned to baseline, then resume treatment at the same dose level or reduce the dose by 1 level at the discretion of the investigator.	Withhold dose until toxicity is Grade ≤ 1 , or has returned to baseline, then reduce the dose by 1 level and resume treatment, or discontinue at the discretion of the investigator.
Hematologic	Continue at the same dose level.	Continue at the same dose level.	Withhold dose until toxicity is Grade ≤ 2 , or has returned to baseline, then resume treatment at the same dose level.	Withhold dose until toxicity is Grade ≤ 2 , or has returned to baseline, then reduce the dose by 1 level and resume treatment or discontinue at the discretion of the investigator.

Specific GI toxicities potentially related to PF-07265028 should be managed according to the dose modifications described in [Table 9](#).

090177e198aafefApproved\Approved On: 22-Nov-2021 20:52 (GMT)

Table 9. Dose Modifications for PF-07265028 Related GI Toxicity

Grade 1	Grade 2	Grade 3*	Grade 4
Continue at the same dose level and, institute standard of care supportive measures at the discretion of the investigator.	Continue at the same dose level and institute standard of care supportive measures at the discretion of the investigator. If recurrent and intolerable, withhold dose until toxicity is Grade ≤ 1 , or has returned to baseline, then resume treatment at the next lower dose level	Withhold dose until toxicity is Grade ≤ 1 , or has returned to baseline, then resume treatment at the same dose level or reduce the dose by 1 level at the discretion of the investigator. If recurrent, withhold dose until toxicity is Grade ≤ 1 , or has returned to baseline, then reduce the dose by 1 level.	Withhold dose until toxicity is Grade ≤ 1 , or has returned to baseline, then reduce the dose by 1 level and resume treatment, or discontinue at the discretion of the investigator. If recurrent, permanently discontinue treatment

*Nausea, vomiting, or diarrhea must persist at Grade 3 despite optimal supportive care to require dose modification.

Note: Cycle will not be extended to cover for the missing dose.

Note: For management of GI iRAEs see [Appendix 3 Section 10.3](#).

Note: Participants with confirmed Hy's Law must be discontinued.

Table 10. Dose Modifications for PF-07265028 Related QTcF Prolongation

QTcF >480 ms \leq 500 ms	QTcF >500 ms	Recurrent QTcF >500 ms	QTcF >500 ms or >60 ms change from baseline, and Torsade de pointes or polymorphic ventricular tachycardia or signs/symptoms of serious arrhythmia
Reduce the dose of drug by one level without interruption of dosing. Following dose reduction, the drug dose may be resumed at the previous level in the next cycle if the QTcF has decreased to within 30 ms of baseline or <450 ms but subject must be monitored closely for QT prolongation for the first cycle at the increased dose.	Withhold dose for up to 14 days. If QTcF returns to within 30 ms of baseline or <450 ms within 14 days, resume and reduce by 1 dose level.	Permanently discontinue treatment if QTcF >500 ms recurs despite appropriate dose reduction and correction/elimination of other risk factors (eg, serum electrolyte abnormalities, concomitant QT prolonging medication)	Permanently discontinue treatment

Note: For all episodes of QTc prolongation, regardless of grade, check electrolyte (potassium, calcium, and magnesium) levels and correct any abnormalities. If possible, stop any medications that may prolong the QT interval (see [Section 8.2.4](#) for management of QTc prolongation).

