
Grade 3 to 4 Grade 3: Covering $>$30% body surface area; Grade 4: Life threatening consequences
	
 -Withhold study treatment for Grade 3. -Permanently discontinue for Grade 4 or recurrent Grade 3. -Consider skin biopsy -Dermatology consult -1.0 to 2.0 mg/kg/day prednisone or equivalent -Add prophylactic antibiotics for opportunistic infections 	
 -If improves to Grade \leq1: -Taper steroids over at least 1 month; resume study treatment following steroids taper (for initial Grade 3).

090177e198aafefApproved\Approved On: 22-Nov-2021 20:52 (GMT)

Pulmonary irAEs		
Grade of Pneumonitis (NCI-CTCAE v5.0)	Initial Management	Follow-up Management
Grade 1 Radiographic changes only	-Consider withholding study treatment -Monitor for symptoms every 2 to 3 days -Consider Pulmonary and Infectious Disease consults	-Re-assess at least every 3 weeks -If worsens: Treat as Grade 2 or Grade 3 to 4.
Grade 2 Mild to moderate new symptoms	-Withhold study treatment -Pulmonary and Infectious Disease consults -Monitor symptoms daily; consider hospitalization -1.0 to 2.0 mg/kg/day prednisone or equivalent -Add prophylactic antibiotics for opportunistic infections -Consider bronchoscopy, lung biopsy	-Re-assess every 1 to 3 days If improves: -When symptoms return to Grade ≤ 1 , taper steroids over at least 1 month, and then resume study treatment following steroids taper -If not improving after 2 weeks or worsening: Treat as Grade 3 to 4.
Grade 3 to 4 Grade 3: Severe new symptoms; New/worsening hypoxia; Grade 4: Life-threatening	-Permanently discontinue study treatment. -Hospitalize. -Pulmonary and Infectious Disease consults. -1.0 to 2.0 mg/kg/day prednisone or equivalent -Add prophylactic antibiotics for opportunistic infections -Consider bronchoscopy, lung biopsy	-If improves to Grade ≤ 1 : -Taper steroids over at least 1 month -If not improving after 48 hours or worsening: Add additional immunosuppression (for example, infliximab, cyclophosphamide, IV immunoglobulin, or mycophenolate mofetil)

090177e198aafefApproved\Approved On: 22-Nov-2021 20:52 (GMT)

Hepatic irAEs		
Grade of Liver Test Elevation (NCI-CTCAE v5.0)	Initial Management	Follow-up Management

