Grade 1 Grade 1 AST or ALT > ULN to 3.0 x ULN if baseline was normal, >1.5-3.0 x baseline if baseline was abnormal; and/or Total bilirubin > ULN to 1.5 x ULN if baseline was normal, >1.0-1.5 x baseline if baseline was abnormal	-Continue study treatment	-Continue liver function monitoring -If worsens: Treat as Grade 2 or 3 - 4.
Grade 2 AST or ALT >3.0 to ≤5 x ULN if baseline was normal, >3.0-5.0 x baseline if baseline was abnormal; and/or total bilirubin >1.5 to ≤3 x ULN if baseline was normal, >1.5-3.0 x baseline if baseline was abnormal	-Withhold study treatment -Increase frequency of monitoring to every 3 days.	-If returns to Grade ≤1: -Resume routine monitoring; resume study treatment. -If elevation persists >5 to 7 days or worsens: -Treat as Grade 3 to 4.
Grade 3 to 4 AST or ALT >5 x ULN if baseline was normal, >5.0 x baseline if baseline was abnormal; and/or total bilirubin >3 x ULN if baseline was normal, >3 x baseline if baseline was abnormal	-Permanently discontinue study treatment -Increase frequency of monitoring to every 1 to 2 days -1.0 to 2.0 mg/kg/day prednisone or equivalent -Add prophylactic antibiotics for opportunistic infections -Consult gastroenterologist/hepatologist -Consider obtaining MRI/CT scan of liver and liver biopsy if clinically warranted	-If returns to Grade ≤1: -Taper steroids over at least 1 month -If does not improve in >3 to 5 days, worsens or rebounds: -Add mycophenolate mofetil 1 gram (g) twice daily -If no response within an additional 3 to 5 days, consider other immunosuppressants per local guidelines.

090177e198aafefApproved\Approved On: 22-Nov-2021 20:52 (GMT)

Renal irAEs		
Grade of Creatinine Increased (NCI-CTCAE v5.0)	Initial Management	Follow-up Management
Grade 1 Creatinine increased > ULN to 1.5 x ULN	-Continue study treatment	-Continue renal function monitoring -If worsens: Treat as Grade 2 to 3 or 4.
Grade 2 to 3 Creatinine increased >1.5 and ≤6 x ULN	-Withhold study treatment -Increase frequency of monitoring to every 3 days -1.0 to 2.0 mg/kg/day prednisone or equivalent. -Add prophylactic antibiotics for opportunistic infections -Consider renal biopsy	-If returns to Grade ≤1: -Taper steroids over at least 1 month, and resume study treatment following steroids taper. -If worsens: -Treat as Grade 4.

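### Table 8 has no exclusion or precedence rule for immune-related events, so it contradicts Section 10.3.5 for Grade 3 pneumonitis and isolated Grade 3 hepatic elevation

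*Protocol*

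**What the plan says.** Section 6.5 sets the scope of Table 8 in one sentence: "Toxicities potentially related to PF-07265028 should be managed according to the dose modifications described in Table 8". Nothing in that sentence, the table title or the cells removes irAEs. For a Grade 3 nonhematologic toxicity the table says to hold the drug until recovery to Grade 1 or baseline, "then resume treatment at the same dose level or reduce the dose by 1 level at the discretion of the investigator". Discontinuation is not listed in that cell.

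Section 10.3.5, the irAE guidance, says for Grade 3 to 4 pneumonitis: "Permanently discontinue study treatment. -Hospitalize. -Pulmonary and Infectious Disease consults". For Grade 3 to 4 liver test elevation it says: "Permanently discontinue study treatment -Increase frequency of monitoring to every 1 to 2 days". Both act on study treatment. Section 6 of the protocol defines study intervention as both agents, and SAP Section 6.1.2 uses study treatment to cover PF-07265028 and sasanlimab.

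The neighbouring tables do deal with the overlap. Table 11 excludes irAEs in its title, and its Grade 3 and Grade 4 nonhematologic rows send suspected immune-related toxicity to Section 10.3.5. Table 9 has a cross-reference for gastrointestinal irAEs and a note that confirmed Hy's Law cases must stop.

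**The concern.** An event can be both immune-related and potentially related to PF-07265028, and the protocol expects this: the PF-07265028 risk table in Section 2.3.1 opens with immune-related toxicity, and irAEs are part of a primary endpoint in both parts. For such an event outside the gastrointestinal tract, two safety rules apply and the protocol does not rank them.

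The practical risk is a rechallenge. A participant with Grade 3 immune-related pneumonitis who recovers to Grade 1 would go back on PF-07265028 under Table 8, while Section 10.3.5 would have stopped it for good. In a multicenter first-in-human study without a data monitoring committee, sites could manage the same event differently. That affects participant safety, and it also affects the exposure and discontinuation data behind dose selection.

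**Working it through.** The plan gives no figure to reproduce; this is a comparison of texts. I took the graded, non-gastrointestinal categories in Section 10.3.5, first occurrence only, at Grades 2 to 4: rash, pneumonitis, hepatic outside Hy's Law, endocrine, and other. That gives 5 × 3 = 15 cells.

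| Event | Table 8, nonhematologic row | Section 10.3.5 | Result |
|---|---|---|---|
| Grade 3 pneumonitis | hold, then resume at same or one lower dose | permanent stop | contradiction |
| Grade 3 hepatic | same cell | permanent stop | contradiction |
| Grade 2 pneumonitis | continue | "Withhold study treatment -Pulmonary and Infectious Disease consults" | looser |
| Grade 2 hepatic | continue | "Withhold study treatment -Increase frequency of monitoring to every 3 days" | looser |
| Grade 2 other | continue | withhold | looser |
| Grade 4 rash | "then reduce the dose by 1 level and resume treatment, or discontinue at the discretion of the investigator" | "Permanently discontinue for Grade 4 or recurrent Grade 3" | looser |
| Grade 4 pneumonitis, hepatic, other | same cell as Grade 4 rash | permanent stop | looser (3 cells) |
| Grade 2 and 3 rash; Grade 2, 3 and 4 endocrine; first Grade 3 other | continue, or hold then resume | same direction | compatible (6 cells) |

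Count: 2 contradictions + (3 Grade 2 + 4 Grade 4) looser + 6 compatible = 2 + 7 + 6 = 15.

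A cell is called looser when a site can satisfy both texts. At Grade 2, Section 6.5.2 leaves management to medical judgment, so withholding does not breach Table 8. At Grade 4, Table 8 itself allows discontinuation. Compatible means the same direction; for rash and other irAEs at Grade 3, Section 10.3.5 also requires a steroid taper before resuming.

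Two areas are left out because other text largely settles them.
- Confirmed Hy's Law cases must be discontinued (note under Table 9).
- Creatinine: Grade 2 in Section 10.3.5 starts above 1.5 × ULN. From a baseline at or below ULN, the rise is more than 0.5 × ULN. Assuming a ULN of 0.8 to 1.3 mg/dL, that is more than 0.40 to 0.65 mg/dL. If confirmed on repeat and without another cause, it meets the 0.4 mg/dL discontinuation threshold in Section 7.1.2.

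Other text that might settle the two contradictions:
- Section 6.8.3.3 says where the irAE guidelines are, without ranking them.
- Section 2.3.1 sends interruption, reduction and discontinuation for immune-related toxicity to Section 6.5.1, the sasanlimab section.
- Section 6.5.1 introduces the algorithms for early management of suspected organ toxicities, so it applies from onset, but describes them as for sasanlimab irAEs. Its closing paragraph applies once dose modification has failed.
- Section 6.5.4 ends study treatment after more than 8 weeks off sasanlimab. This acts late and only in combination: about 30 in Part 1B plus up to 4 × 40 = 160 in Part 2A. It cannot reach monotherapy: about 30 in Part 1A plus up to 20 in Part 2B, or 50/240 = 21% of maximum enrolment.
- Section 6.5.2 makes resumption after a DLT depend on investigator and sponsor opinion that the participant is benefiting. DLTs belong to Cycle 1 of Part 1: about 60/240 = 25% of participants, and 28/730 = 3.8% of a 24-month treatment period. The condition still permits resumption one level lower.

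**The case against.** The best reply is that a specific rule beats a general one. Section 10.3.5 is organ-specific, Table 8 is a generic two-row table, and three sections point toward the irAE guidance; the Section 2.3.1 pointer even covers discontinuation. Sections 4.1 and 7.1 allow an investigator to stop one or both agents for toxicity, and Section 8 requires immediate sponsor discussion of safety issues. In combination, a permanent sasanlimab stop would also end PF-07265028 after 8 weeks under Section 6.5.4.

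Much of this stands. A careful reader would probably follow Section 10.3.5, and nobody is forced to rechallenge. But that result is inferred. No sentence gives Section 10.3.5 precedence over Table 8, resumption within the 8 weeks stays open, and monotherapy has only the unranked pointers.

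A reader might go further and treat all nine non-compatible cells as contradictions. The documents do not support that: medical judgment at Grade 2 and the discontinuation option at Grade 4 let a site meet both rules. Nor do they support the inference that the protocol has no irAE rule for PF-07265028, since Section 10.3.5 acts on study treatment.

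The general nonhematologic DLT criterion in Section 4.3.3.2 is printed as Grade above 3. The exemption of isolated Grade 3 laboratory abnormalities in Section 4.3.3.3 suggests that Grade 3 may be intended. Either way, Section 6.5.2 would only condition resumption in Cycle 1 of Part 1; it would not prevent it.

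**Conclusion.** The point holds for two cells of 15: Grade 3 pneumonitis and isolated Grade 3 hepatic elevation outside Hy's Law. There the two texts give opposite instructions and nothing in the protocol states which prevails. In 7 further cells Table 8 is looser than Section 10.3.5 without strict contradiction.

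This rests on reading study treatment in Section 10.3.5 as including PF-07265028, and on an event being judged both immune-related and potentially PF-07265028-related. The count covers first occurrences in graded categories; the separate rules for recurrent Grade 3 events and for myocarditis are outside it. The documents give no rate for such events, so their expected number cannot be stated. The change should be made because the consequence is a possible unsafe rechallenge and the correction is cheap. It does not call the dose-escalation model or the analyses into question.

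**What to change.** Add *(Excluding irAEs)* to the title of Table 8, matching Table 11, and put one note under it with three statements:

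1. Suspected irAEs are managed by Section 10.3.5, which takes precedence over Tables 8 and 9 for PF-07265028 in combination.
2. Whether the same applies to monotherapy (Parts 1A and 2B). Section 6.5.1 presents the algorithms as for sasanlimab irAEs, so extending a permanent stop to monotherapy is a clinical decision that the sponsor must make explicitly.
3. A hold that passes 4 weeks because of the steroid taper is handled by the existing benefit/risk exception in Section 6.5.4, after sponsor discussion.

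The third statement is needed because, where Section 10.3.5 calls for a taper, it lasts at least 1 month and begins only once the event is improving. With recovery time t and a taper of at least 28 days, the hold is at least t + 28 days, which exceeds the 28-day limit for any t above zero.

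The cost is one title and one note, with no added visits, procedures or participants. The downside is small: some participants will stop PF-07265028 permanently, or be held longer, where Table 8 would have let them resume.
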